Participants who are interested in learning more about the fMRI sub-study will indicate so on the main study consent form. A member of the research team will explain the sub-study to the participant and guardian(s). If the participant is willing to participate, the sub-consent and assent forms will be completed. [name] will complete a psychological history for all participants who agree to participate in the fMRI sub-study. Female participants in the experimental group (Nausea group; n=15 and IBS group; n=15) who are found to be eligible to participate in the sub-study will be scheduled to complete the fMRI scans at Visit 3 (baseline scan) prior to EAD placement and Post #1 (post-scan; day 5 after the last neurostimulator placement within one hour of removing the device). The post-scan will be compared to baseline and baseline scans from 15 age-and gender-matched healthy controls who will undergo one fMRI scan (no therapy). All ethnic categories will be included.

Healthy control participants will be recruited via word of mouth. Researchers will mention the study to peers who will be instructed to contact the research team to learn more about the study. A member of the research team will introduce the study either in person or over the phone and will explain the inclusion and exclusion criteria. If the participant is eligible, consent/assent documents will be completed. Participants will then be scheduled to visit the pTRU where they will meet with a study physician who will perform a brief medical examination to confirm participant eligibility. Eligible participants will be escorted to the MRI unit by a member of the research team where they will be introduced to the mock scanner. Participants will have the option of lying in the mock scanner prior to their fMRI scan. A medical professional who is a member of the research team will be present during the scan. Healthy controls will only have 1 fMRI visit which will be completed at their convenience.

fMRI Sub-study inclusion (FN and IBS Groups):

- meet general study inclusion criteria

fMRI Sub-study inclusion (Healthy Control Groups):

- Female children, aged 12 years to 18 years, who provide written assent and whose parents provide written permission for participation
- English-speaking

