All these imaging protocols and data acquisition will be completed within one scanning sessions in 30 min for each subject.

Data Acquisition and Analysis

Data acquisition: The cerebral cortical activity will be monitored in all subjects with a blood oxygenation level-dependent (BOLD) fMRI technique. Gradient echo-planar imaging (EPI) data will be acquired on a Neuro-optimized 3.0 T MR system (General Electric, Milwaukee, WI, USA). A quadrature birdcage head coil will be used for radio frequency (RF) transmission and reception. One hundred and twenty T2*- weighted images depicting blood oxygenation level-dependent (BOLD) contrast (Ogawa et al., 1990) will be acquired over 6 min at each of 14 near-axial non-contiguous 4 mm thick planes parallel to the inter commissural (AC±PC) line: TE (echo time) = 25 ms; TR (repetition time) = 2 s; matrix size = 64 x 64; FOV (Field of view) = 240 mm; in-plane resolution = 3.75*3.75 mm²; interslice gap = 0.7 mm.

Scanning protocol: A 6 min resting state scan will be performed at baseline. The same protocol is repeated at end of therapy with another scan after device is removed (Table 1; post-neurostimulation #1). This will allow us to examine functional connectivity changes induced by the stimulation. rsFC will be compared between baseline and end of treatment in both treatment responders and non-responders and compared to healthy controls and IBS patients. Brain activation will be quantified for each voxel by measuring percent change of BOLD signal relative to the baseline. Spatial smoothing of the response magnitude across voxels will be

conducted using a 6-mm full-width half-maximum (FWHM) Gaussian kernel filter to compensate for intersubject variability. In the group analysis, activation maps for each stimulation state and group will be derived by applying voxelwise one-sample *t*-tests of fitting coefficient from regression analysis. The obtained statistical maps were corrected for multiple comparisons using the probability and cluster thresholding technique (AlphaSim in AFNI).

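### Family-wise error control of the voxelwise fMRI maps is not assured: AlphaSim is named without a smoothness input or voxelwise threshold, and a permutation threshold is a cheap improvement

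*Combined protocol and SAP*

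**What the plan says.** The multiplicity control for the voxelwise maps is set out in the Data Acquisition and Analysis section (under F). The response maps are smoothed with a "6-mm full-width half-maximum (FWHM) Gaussian kernel filter to compensate for intersubject variability". Then "activation maps for each stimulation state and group will be derived by applying voxelwise one-sample *t*-tests of fitting coefficient from regression analysis". The resulting maps are "corrected for multiple comparisons using the probability and cluster thresholding technique (AlphaSim in AFNI".

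That section gives no voxelwise p, minimum cluster size, map-level alpha, sidedness or search mask, and it does not say what smoothness AlphaSim receives. The later fMRI analyses section lists seed-based, region-based and whole-brain network analyses and adds no threshold. The 0.05 cut-off in section O is general and is not tied to the maps.

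The sample is given under Optional fMRI Sub-study: "Female participants in the experimental group (Nausea group; n=15 and IBS group; n=15", with "baseline scans from 15 age-and gender-matched healthy controls who will undergo one fMRI scan (no therapy". The images are acquired "at each of 14 near-axial non-contiguous 4 mm thick planes", with "in-plane resolution = 3.75*3.75 mm²; interslice gap = 0.7 mm".

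**The concern.** AlphaSim finds the cluster size that pure noise would rarely exceed. The noise that it simulates is white noise smoothed with a Gaussian kernel. This is a property of the method; the documents do not describe it. Two things can make the resulting cluster size too small:

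- The width entered is smaller than the true smoothness of the images. The kernel adds to whatever smoothness the images already have, so entering the kernel width understates the total unless the unsmoothed noise has no spatial correlation at all.
- The true spatial correlation falls off more slowly than a Gaussian, so that no single width describes it.

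The size of either effect depends strongly on the voxelwise p. The plan fixes neither the width nor the p. Aim 2 and part of hypothesis 3b are connectivity claims, and a map labelled as corrected will be read as carrying a 5% chance of any false cluster.

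**Working it through.** The plan states no map-level error rate, so there is no figure to reproduce. The check asks what error rate a nominal 5% AlphaSim threshold would have under settings that the plan leaves open.

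**From the documents:** voxels 3.75 × 3.75 mm in plane; slice spacing 4 + 0.7 = 4.7 mm; 14 slices; 6-mm kernel; one-sample t-maps of 15 subjects (14 df).

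**Assumed:** elliptical mask of 16,632 voxels, face-connected clusters, positive clusters only, target 5%, voxelwise p of 0.05, 0.01, 0.005 or 0.001, and the true smoothness.

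**Step 1, total smoothness.** For Gaussian smoothness, total width = √(6² + w²), where w is the width before the kernel is applied. With w = 0, 3.8, 4.5, 5 and 8 mm the total is 6.0, 7.1, 7.5, 7.8 and 10.0 mm. Only w = 0 makes 6 mm the right input.

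**Step 2, cluster threshold.** From 1,500 simulated noise fields, take the smallest k with P(largest cluster ≥ k) ≤ 0.05.

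**Step 3, actual error.** In 500 null experiments, form t = mean / (SD/√15) at each voxel. Count the share with any cluster of at least k voxels. The Monte Carlo SE at 5% is √(0.05 × 0.95 / 500) ≈ 1 point.

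Each cell runs over voxelwise p 0.05 / 0.01 / 0.005 / 0.001.

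| True width (mm) | k needed (voxels) | Error, 6 mm entered (%) | Error, true width entered (%) |
|---|---|---|---|
| 6.0 | 41 / 12 / 9 / 5 | 2.2 / 2.4 / 0.6 / 0.6 | same |
| 7.1 | 74 / 19 / 13 / 7 | 38.8 / 22.8 / 13.8 / 9.0 | 2.0 / 2.8 / 2.6 / 1.4 |
| 7.8 | 98 / 25 / 18 / 9 | 70.6 / 50.8 / 34.8 / 15.2 | 2.2 / 2.8 / 1.4 / 0.4 |
| 10.0 | 183 / 44 / 31 / 14 | 99.0 / 95.8 / 82.8 / 49.2 | 4.0 / 3.4 / 2.0 / 1.2 |

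Three separate simulations with 6 mm entered and a true width of 7.5 mm gave 30%, 45% and 40% at p 0.01, and 12%, 13% and 16% at p 0.001. The spread at p 0.01 is more than Monte Carlo error (√(0.45 × 0.55 / 300) ≈ 3 points), so the percentages are sensitive to set-up. All lie well above 5%.

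**Step 4, long tails.** Two assumed cases, each with a single Gaussian width entered:

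- 80% of variance at 6 mm and 20% at 20 mm. The width estimated from the simulated fields is 6.44 mm. The error is 52.6 / 10.8 / 9.2 / 1.4% at the four voxelwise p values.
- 20% of variance at 18 mm on a 7.5-mm core, with 7.5 mm entered. Three simulations gave 19%, 16% and 17% at p 0.01, and 4%, 5% and 4% at p 0.001.

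**Step 5, the alternative.** A sign-flipping threshold was tried on 15-subject null maps at p 0.01 / 0.001. One simulation gave 3.0 / 2.7% in the Gaussian case and 6.0 / 3.3% in the long-tailed case (SE about 1.3 points). Another gave 4.7 / 2.0% and 7.3 / 2.0% (SE about 2 points). The highest value, 7.3%, is (7.3 − 5)/2 ≈ 1.2 SE above 5%.

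**The case against.** The strongest objection is that the plan never says that 6 mm goes into AlphaSim. The kernel is described as a preprocessing step for differences between subjects. If the analysts enter the true width, the table shows errors of 0.4% to 4.0% at every voxelwise p. Even with long tails, p 0.001 gave about 1–5%. This stands. A reader might infer from the sentence that the stated correction fails, or that every corrected cluster carries an error of several times 5%. The documents do not support that, because the outcome depends on two settings that they leave open.

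A reader might also blame the 15-subject maps. That is not supported either: with the width right, the 14-df maps stayed below 5%.

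The percentages rest on assumed smoothness, tails, mask and voxelwise p. They use the acquisition grid, whereas the fMRI analyses section converts the data to MNI templates before group analysis, and the Multimodal Imaging protocols section describes a different coil and pulse sequence. The exact figures could therefore move. The direction would not, since the required cluster size rises with smoothness.

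Finally, the AlphaSim sentence follows one-sample maps, while the main hypotheses are contrasts for a named amygdala-vmPFC pair. Two-sample contrasts were not simulated. A prespecified region-of-interest test of that pair would need no cluster correction. This limits the reach of the point, but the seed-based and whole-brain maps remain planned and need a threshold.

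**Conclusion.** The point holds in conditional form. The plan names a cluster correction whose validity depends on a smoothness input and a voxelwise p that it does not give, so control of the family-wise error rate is not assured.

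- If the 6-mm kernel is the input and the images are smoother (assumed 7.1 to 7.8 mm), the error is about 23–51% at voxelwise p 0.01 and 9–16% at p 0.001.
- If a suitable single Gaussian width is entered but the spatial correlation has long tails (assumed), it is about 11–19% at p 0.01 and 1–5% at p 0.001.
- If the correct Gaussian width is entered and there is no long tail, it is at or below 5%.

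The point is confined to the voxelwise maps of an optional sub-study and does not touch the Nausea Severity Scale result. The change is worth making because it is cheap and takes away the dependence on the smoothness input.

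**What to change.** Replace the AlphaSim sentence in Data Acquisition and Analysis with wording such as:

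*Cluster-level family-wise error is controlled at 5% by permutation: sign-flipping for one-sample and paired maps, and permutation of group labels for two-sample maps, with 5,000 permutations and a cluster-forming threshold of p<0.001. The tests are [one- or two-sided] and the search mask is [named].*

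If simulation is kept, state that the spatial correlation is estimated from the residuals with a form that allows long tails, and use p<0.001. State the sidedness, mask and 5% map-level alpha in this case too.

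With 15 subjects there are 2^15 = 32,768 sign patterns, so 5,000 random ones are available. The responder and non-responder maps will have fewer: 7 subjects, for example, give 2^7 = 128, and all of them should then be used.

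The cost is a change of wording and some computing time, and somewhat fewer clusters will pass correction. Nothing changes in scanning or sample size.

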Medical and psychological history will be obtained to verify eligibility and screen patients for alcohol, nicotine, and drug abuse following the completion of consent/assent documents. All eligible subjects will complete the questionnaires related to demographic, medical, and psychological factors including nausea, abdominal pain, IBS symptoms (Rome IV), anxiety, disability and quality of life (Table 1). This will take about 30 minutes total to complete. Subjects will then undergo baseline heart rate variability (HRV) measurements in clinic. Children will perform a self-assessment of the Tanner stage of pubertal development using a validated self-assessment form.

Visit 1: Subjects will undergo the ¹³C gastric emptying breath test (GEBT) (Table 1). See section on ¹³C GEBT for details and attached protocol.

Visit 2: Subjects will undergo Satiety Drink Test (see SDT section and attached protocol).

Visits 3-6: Subjects will complete questionnaires as per Table 1 followed by neurostimulator placement by study physician. These visits will be repeated weekly and take about 20-40 minutes to complete. HRV will be measured before and after the EAD placement at Visit 3 and 6.

Post-neurostimulation #1: Subjects will not return but will complete questionnaires (Table 1) at the end of 4 weeks of therapy which will be mailed back to the research team. Participants in fMRI sub-study will undergo repeat fMRI scan (post-scan) at this visit and complete questionnaires per Table 1.

Post-neurostimulation #2: All subjects will return to clinic for their regularly scheduled clinic follow-up visit 2 months after end of therapy and will complete questionnaires as per Table 1.

Subsequent to the initial 4 weeks of therapy, subjects will undergo another 4 weeks of **active neurostimulation therapy (visits 7-10) with the exact same protocol as during the first round of treatment. A post-neurostimulation #3 questionnaire assessment will be completed (just as with post-neurostimulation #1) although no repeat fMRI scans will be performed at this time. Similarly, a post-neurostimulation #4 clinic visit will be scheduled 2 months after the end of the second 4 week of therapy.

Optional fMRI Sub-study

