Subjects will be randomized in a 1:1 ratio to either treatment or sham group. Randomization will be determined using a computer program based on random number generation in blocks of 10 subjects at a time. The manufacturer will provide the researchers with four devices per package (4 weeks per patient) and distribute 10 packages at a time to the investigators. Each package will have a serial number and only one research coordinator will have the key to which serial numbers represent active devices and which represent inactive ones. This research coordinator will keep the data in a secure database and will not be involved in any of the patient recruitment or study procedures. All other research coordinators, investigators, statistician and nurses involved will be blinded. Research coordinators within the division of gastroenterology will store the devices as pre-packaged by manufacturer and label the devices with a serial number and patient ID number. A labeled folder for each patient with all questionnaires needed for the entire study will also be kept with each subject package. The devices and folders will be stored in a locked office in the gastroenterology division, only accessible by research coordinators. Password protected iPads will be used to collect questionnaire information from participants. No PHI will be loaded on these iPads.

A blinded research coordinator will bring each subject's numbered package to the research area (Translational Research Unit) when patient arrives. The package for the subject will be stored locked in the TRU until the subject finishes the 4 week therapy. The coordinator will ask the subject to complete the pre-placement questionnaires (Table 1; visit #3) and hand the device (numbered with serial # and patient ID only) to one of the certified MDs for placement. The devices will be "made to order" when requested by the PI and will be shipped packaged as above.

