Aim 3. *Hypothesis 3a): Four weeks of active neurostimulation will reduce nausea and concurrent symptoms from baseline compared to sham therapy as measured by weekly Nausea Severity Scale total score (primary outcome) after 4 weeks of therapy. Secondary outcomes include daily nausea (BARF) scores, and weekly nausea profile scores, upper GI symptoms (PAGI-SYM), abdominal pain (API), anxiety (SUDS, PROMIS and VSI), quality of life (PROMIS), disability (FDI) and co-morbid symptoms (CSI).* Another secondary efficacy variable will be the change in Nausea Severity Scale score after the second 4 weeks of therapy in a subset of subjects. We will compare pre and post total nausea, GI symptoms, anxiety, disability, quality of life and co-morbid symptom scores using a two-sided paired *t*-test at a Bonferroni corrected alpha of 0.05. Power: with ~40 in each group initially, allowing for 12% dropout based on our prior study, we will have ~35 subjects and 80% power to detect a difference of at least XX standard deviations (SD). We will similarly compare the other variables. Further we will use regression and regression trees with final value as the outcome and demographics, baseline values and overall symptoms as covariates. *Hypothesis 3b: Adolescents with FN will have reduced vagal tone as measured by HRV. Active neurostimulation therapy will elevate vagal tone compared to baseline and sham therapy, resembling that of healthy controls.* We will similarly analyze the change in vagal tone in nausea subjects. Further we will compare

the final vagal tone to healthy using a two sample t-test of equivalence where equivalence will be defined as within 20%. See fMRI analysis section for details on resting state fMRI analyses.

Longitudinal Continuous Variables

The efficacy parameters of longitudinal continuous variables such as nausea and pain will be analyzed using a mixed effects covariance pattern model to utilize all the data collected over time with consideration of the variance-covariance matrix of the repeated measures. This method allows a general unstructured variance-covariance matrix and allows patients to have incomplete data across scheduled time points. The method applied is also known as mixed-effects repeated measures analyses (MMRM).

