The primary model will include independent variables of the fixed, categorical effects of treatment, assessment visit, and treatment-by-assessment, interaction, along with the continuous effects of baseline and baseline-by-assessment interaction up to end of study. An unstructured variance-covariance structure will be used to model the within-patient errors and different variance-covariance structures will be tried for goodness-of-fit exploration.

Continuous/ Ordinal variables

Summary statistics such as mean, median, standard deviation, range and correlation plots and tree analysis will be used to examine distributions and interrelationships. Where necessary, for parametric assumption, we will employ appropriate transformations with justifications. If data cannot be appropriately transformed we will compare variables between the two groups using a Mann-Whitney test.

Additional Analysis

In addition to the above described primary analysis, the following analysis will be done.

1. The mean change from baseline in all efficacy variable scores will be summarized using descriptive statistics at all assessment time points.
2. To assess effects of dropouts, the dropout cohort analysis will be performed by summarizing the change of primary and secondary efficacy variables using different dropout cohorts. Dropout cohorts will be formed by patients that had their last primary efficacy measurement in the same assessment interval.

For all efficacy variables, nominal p-values will be presented without applying any adjustment for multiple comparisons.

GEBT Metrics

The preferred and FDA approved GEBT metric is the Percent Dose (abbreviated PCD) excreted at time t after consumption of the test meal. To provide a more convenient scale, we multiply PCD by 1000 to produce kPCD at any time, t.

$$kPCD_t = \left[\frac{DOB * CO_2 PR * R_s * 13}{10 * dose} \right] * 1000$$

where:

- DOB = The measured difference in the ratio [$^{13}\text{CO}_2/^{12}\text{CO}_2$] between a post-meal breath specimen at any time (t-minutes) and the baseline breath specimen.
- CO₂PR = CO₂ Production Rate (mmol CO₂/min) calculated using the Schofield equations⁹⁷ which incorporate the patient's age, gender, height and weight.
- R_s = The ratio [$^{13}\text{CO}_2/^{12}\text{CO}_2$] in the reference standard (Pee Dee belemnite) for these measurements. R_s = 0.0112372
- 13 = the atomic weight of Carbon-13
- 10 = A constant factor for converting units

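### The second-course nausea change is listed as an efficacy variable but has no concurrent sham, no stated starting point, subset rule or handling of original arm; from study entry it can be significant through first-course change alone

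*Combined protocol and SAP*

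**What the plan says.** Section F, Statistical Analysis, Power, Aim 3 (Hypothesis 3a) adds a second-course variable to the secondary outcomes: "Another secondary efficacy variable will be the change in Nausea Severity Scale score after the second 4 weeks of therapy in a subset of subjects". The next sentence gives the method, a t-test: "We will compare pre and post total nausea, GI symptoms, anxiety, disability, quality of life and co-morbid symptom scores using a two-sided paired". The significance level is set there too: "at a Bonferroni corrected alpha of 0.05". Additional Analysis says otherwise on multiplicity: "For all efficacy variables, nominal p-values will be presented without applying any adjustment for multiple comparisons".

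The second course is described in section D, Protocol and Procedures. After the first four weeks, subjects receive "active neurostimulation therapy (visits 7-10) with the exact same protocol as during the first round of treatment". Nobody is excluded by first-course arm, and no sham is mentioned. On the end-of-course measurement: "A post-neurostimulation #3 questionnaire assessment will be completed (just as with post-neurostimulation #1"), with a Post #4 visit two months after that course. Table 1 stops at Post #2 and shows neither Visits 7-10 nor Post #3.

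The first course is randomised: "Subjects will be randomized in a 1:1 ratio to either treatment or sham group" (Auricular Neurostimulation treatment protocol).

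**The concern.** An efficacy variable should be able to separate the effect of the treatment it describes from everything else that moves the score. This one cannot. Everyone measured has just had active stimulation, and four things needed to interpret the change are missing:

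- **Starting point.** Study entry, Post #1, Post #2 and the start of the second course are all possible. From study entry, the change contains the whole first-course response.
- **Subset.** Protocol and Procedures reads as though all subjects take the second course; the Aim 3 text says only some. How they are chosen is not stated.
- **Original arm.** Former sham subjects would be having their first active course and former active subjects their second. These are different questions.
- **Test.** The paired comparison beside the variable has no term for randomised arm.

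At stake is a p-value, attached to a variable labelled efficacy, that could reflect sham response, retained first-course benefit, time, expectancy or selection.

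**Working it through.** **The plan's own figure.** About 40 per group with 12% dropout gives 40 × (1 − 0.12) = 35.2, which reproduces the stated ~35. The detectable difference appears only as XX SD, and no sample size or power is given for the second-course variable, so there is nothing more to reproduce.

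**Inputs.** From the documents: a two-sided paired t-test; alpha either nominal 0.05 or Bonferroni corrected. Assumed, because the documents give no values: subset size n = 20, 35 or 70 (35 is one group after dropout, 70 is both); retained first-course improvement d = 0.3 or 0.5 SD of the change score; six tests for Bonferroni, one per score domain in the paired-test sentence, so 0.05/6 = 0.0083. The true second-course effect is set to zero.

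**Case 1: change from study entry.** The paired t statistic has noncentrality d√n and n − 1 degrees of freedom. The chance of significant improvement is the probability that it exceeds the two-sided critical value (2.09, 2.03 and 1.99 at alpha 0.05 for n = 20, 35 and 70; 2.94, 2.80 and 2.72 at 0.0083). For example, d = 0.3 and n = 20 gives 0.3 × √20 = 1.34 against 2.09, a chance of 25%.

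| Retained d | Alpha | n = 20 | n = 35 | n = 70 |
|---|---|---|---|---|
| 0.3 | 0.05 | 25% | 41% | 70% |
| 0.5 | 0.05 | 56% | 82% | 98% |
| 0.3 | 0.0083 | 8% | 17% | 42% |
| 0.5 | 0.0083 | 27% | 57% | 92% |

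With no change at all, the chance of significant improvement is 2.5% at alpha 0.05 and 0.4% at 0.0083. These figures depend only on the mean retained improvement in whatever subset is analysed, so they do not require the arms to be pooled. If they were pooled 1:1, simulation (40,000 runs, alpha 0.05) with first-course changes of 0.3 SD on sham and 0.6 SD on active gives 48%, 79% and 96% for n = 20, 40 and 70. With 0 and 0.5 SD it gives 17%, 32% and 52%.

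**Case 2: change from just before the second course.** First-course change drops out. With an unselected subset and no expectancy or time effect, the chance of significant improvement is 2.5% at every n. Two departures, at alpha 0.05:

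- An assumed open-label drift of 0.2 SD gives 13%, 21% and 38% for n = 20, 35 and 70.
- Suppose the subset is the worse half on the score before the second course, with pre/post correlation ρ. The mean fall from regression to the mean is (1 − ρ)√(2/π), in SD of the score: 0.40 at ρ = 0.5 and 0.16 at ρ = 0.8. In simulation the chance of significant improvement is 45% and 20% at n = 20, and 71% and 32% at n = 35.

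**Does another analysis repair it?** The MMRM under Longitudinal Continuous Variables has treatment and treatment-by-visit terms but is not tied to the second course. If extended to Post #3, it would compare active-then-active with sham-then-active, which does not isolate the second course. The change-from-baseline summaries under Additional Analysis define no new baseline for it.

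**The case against.** The strongest reply is that this is one added secondary variable after a randomised, sham-controlled first course. The primary outcome is untouched, an all-active second course is a legitimate design choice, and any reader of Protocol and Procedures can see that it has no sham. That stands, and it limits the weight of the point.

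A reader might infer that the plan pools former active and former sham subjects, or that it discards the randomisation. The documents do not say so. They are silent: the subset could be one arm, or be reported by arm, and the MMRM does carry a treatment term. What stands is that the handling of original arm is unspecified.

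It can also be said that the paired-test sentence does not name the second course, and that its alpha is Bonferroni corrected. Both are true. It is nevertheless the only test placed beside this variable, and Additional Analysis promises unadjusted p-values for every efficacy variable. The stricter level lowers the figures but does not remove the problem.

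Finally, the percentages are the power to detect a real mean change, not an inflated test size. The fault lies in what the change would be attributed to.

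**Conclusion.** The point holds as a gap in the definition and labelling of a secondary variable. As written, the second-course change cannot show that a second course works, and no other analysis in the plan supplies the missing comparison.

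A reader might go further and conclude that the variable will come out positive from sham response or first-course benefit. The documents do not support that. It can happen if change runs from study entry, which is the only baseline the plan otherwise uses. It does not follow if change runs from just before the second course, where expectancy, natural course and selection of the subset are the remaining biases.

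The sizes in Case 1 rest on assumed retained improvements, subset sizes and number of tests, and those in Case 2 on an assumed drift and correlation. They show what is possible, not what is expected. The primary first-course comparison is not affected.

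**What to change.** - **Define the variable** as change from the last Nausea Severity score before device placement in the second course (Visit 7) to Post #3. A Visit 7 score is implied by "with the exact same protocol as during the first round of treatment", but Table 1 does not show it; add Visit 7 and Post #3 to the table.
- **Report by first-course randomised arm**, with 95% confidence intervals and the number continuing out of those randomised in each arm.
- **Label it open-label and descriptive**, with no efficacy p-value or claim. A within-subject contrast of active against earlier sham change in former sham subjects is exploratory and confounded with order and time. The further change in former active subjects should not be called the added value of a second course.
- **State how the subset is formed**, and reconcile Protocol and Procedures (all subjects) with the Aim 3 text (a subset). The timing of the second course relative to Post #2 must also be made clear, because it determines what a Visit 7 start represents.
- **Reconcile the two multiplicity statements**, Bonferroni and no adjustment.

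The cost is SAP wording and a Table 1 update. If the questionnaires are given as implied, no extra data are needed. The downside is smaller groups and wider intervals than a single combined change would give.
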